Fulvestrant is the only drug promoting the degradation of the estrogen receptor (ER). Despite the fact that fulvestrant has demonstrated superiority over aromatase-inhibitors (AI) and tamoxifen, it is approved only for use in postmenopausal breast cancer patients. In premenopausal patients, tamoxifen or AI with ovarian suppression remains the standard of care only because data supporting the use of fulvestrant in these women is lacking. Significant clinical and laboratory-based data links the cyclinD1-interactome to a proliferative effect of tamoxifen in cyclinD1 positive tumors. CyclinD1 is overexpressed in 35% of breast cancers, and serves as a major hub regulating a large transcriptional network. In addition to its role in cell cycle, the cyclinD1-interactome regulates the ER, metastasis, DNA repair pathways, and stem cell differentiation. While tamoxifen promotes the oncogenic effect of the cyclinD1-interactome, in marked contrast, by degrading the ER, fulvestrant disrupts the cyclinD1-interactome and promotes cell death. We therefore hypothesize that the cyclinD1-interactome can be used to orient the use of fulvestrant in both premenopausal and postmenopausal women. To test this hypothesis, we propose a pre-surgical randomized clinical trial of tamoxifen vs fulvestrant in the window between breast cancer diagnosis on core biopsy and definitive surgery. Women with ER/cyclinD1 positive tumors will be eligible. Response to tamoxifen or fulvestrant will be evaluated using standard proliferation index as well as gene expression signatures obtained in pre-clinical models of tamoxifen resistance and sensitivity to fulvestrant. In addition, we propose to use cutting edge new technology allowing ex-vivo expansion of primary culture from only a few cancer cells obtained by fine needle biopsy. We propose to compare the response of these primary cells to patient response. If successful, this work can support the expansion of use of fulvestrant to not only postmenopausal women but premenopausal women as well. In addition, it may serve as a proof of principle to maximize the use of biopsy material to predict treatment response.

BACKGROUND AND RATIONALE

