To determine whether patient's response to tamoxifen or fulvestrant correlated with response in their primary cells in vitro, cells from primary tumors from patients will be grown in vitro. Proliferation assays over a range of doses in vitro, of the same drug that the patient received will be conducted. Correlations between in vitro assay results and patient assay results will be examined by Pearson correlation or Spearman correlation for data not normally distributed for pre- and post-menopausal patients. Dose response will also be analyzed by regression analysis.

Stopping Rule:

Keeping in mind the potential proliferative effect of tamoxifen, this trial will include an early stopping rule, where if the mean change from baseline in the Ki67 proliferation index among the first fourteen patients in the tamoxifen arm is an increase of at least 25%, that arm of the trial will be terminated. Although fulvestrant is unlikely to cause acceleration of proliferation, the same stopping rule will be applied to the fulvestrant arm as well. A mean increase of 25% in 14 patients would give an 80% confidence interval that the true mean Ki67 increase in a treatment arm is in the range of 16% to 34%.

An additional stopping rule will be implemented based on the number of patients experiencing a high level of proliferation (50% or higher). If 2 of the first 10 patients in a treatment arm experience an increase from baseline in the Ki67 proliferation index of 50% or more, then that treatment arm will be terminated.

PATIENT ELIGIBILITY

Inclusion and Exclusion Criteria

Inclusion criteria:

- Written informed consent prior to beginning specific protocol procedures, including expected cooperation of the patients for the study treatment regimen and follow-up, must be obtained and documented according to the local regulatory requirements
- Adult women greater than 18 years of age
- Eastern Cooperative Oncology Group (ECOG) performance status (PS) 0-2
- New diagnosis of invasive cyclin D1 +, ER+, PR +/-, Her2- breast cancer
 - Cyclin D1 positive as defined as a total immunohistochemical score of 5 or greater
 - Hormone receptor positive as defined as $\geq 10\%$ positive stained cells
 - HER2-normal (IHC score 0-1 or FISH negative [in-situ hybridization (ISH) ratio ≤ 2.0 status])
- Tumor size at least 5 mm with planned primary surgery at Mount Sinai
- A negative urine dipstick pregnancy test

Exclusion criteria:

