The initial core biopsy for routine diagnosis will be performed prior to the 14 day study regimen. Then the subjects will receive 14 days of Fulvestrant or Tamoxifen as described above. After the

Comparison in the Change of Proliferation Index between Fulvestrant and Tamoxifen in Cyclin D1 +, Estrogen Receptor + Breast Cancer

[name], PI

Essential Elements

#13, 09/13/2017

14 day study regimen is complete, the subjects will move on to definitive excisional surgery, between day 15 to day 18, at Mount Sinai, which will be performed at their surgeon's discretion.

CORRELATIVE LABORATORY RESEARCH

Laboratory Determinations and Pathology Review

A study pathologist will determine Ki67 and cyclin D1 status on the initial core biopsy and the excisional surgical specimen. Scoring of the ER, PR and Her2, will be performed using the standard clinical method used for all breast cancer patients at Mount Sinai. For patients with 1+ or higher staining for Her2 on IHC, ISH will be sent. This analysis will be performed by the pathology department as part of the standard clinical management.

The intensity and distribution of cyclin D1 staining will be semiquantitatively scored using the Allred scoring method. The intensity of the immunohistochemical reaction by light microscopy will be recorded as 0 (negative) when no staining of the nuclei is seen even at high magnification, 1+ (weak) if staining is visible only at high magnification, 2+ (moderate) when staining is readily visible at low magnification and 3+ (strong) if staining is strikingly positive even at low power magnification. The extent of tumor cell nuclei showing positive staining will be scored as 0 (<10%), 1 (11-25%), 2 (26-50%), 3 (51-75%), 4 (76-90%), and 5 (>90%). Scores for intensity and extent will then be totaled to assign a tumor as having negative (0), weak (1 to 3), moderate (4 to 6), or strong (7 to 8) cyclin D1 expression as has been standardized by Reis-Filho and colleagues. A total score of greater than or equal to 5 will be used as the cut off for cyclin D1 positivity as per the retrospective study conducted by [name] and colleagues.

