Comparison in the Change of Proliferation Index between Fulvestrant and Tamoxifen in Cyclin D1 +, Estrogen Receptor + Breast Cancer

[name], PI

Essential Elements

#13, 09/13/2017

the cyclinD1 overexpressing tumors in response to fulvestrant compared to the tamoxifen. This analysis will therefore allow us to test this possibility in humans. Further, the analysis of the rate of apoptosis will provide an independent readout of the effect of treatments in addition to proliferation measured by Ki67.

For tumors greater than 1 cm, a small portion of the surgical specimen not needed for diagnostics will be divided: half will be frozen for subsequent RNA extraction and expression profiling, and half will be utilized for primary tissue culture.

For RNA extraction and gene expression profiling, a gene signature that distinguishes cells that are responsive to tamoxifen and those that are resistant to tamoxifen has been established using cell lines in vitro. Similarly, a gene signature of the same cells in response to fulvestrant was also determined. Using these signatures obtained in vitro, we will compare whether the same gene signature characterizes tumors that are resistant or sensitive to tamoxifen and fulvestrant respectively in patients samples using selected gene by nanostring analysis by RNA extraction from paraffin embedded sections.

In order to assess response of a patient's primary cells in vitro, the organoid core facility has recently developed a method by which cells from primary tumors from patients can be grown in vitro. When samples are available for culture in vitro, we will test whether the cells derived from individual patients respond the same as the tumor in vivo in the same patient. For this experiment, cells in culture will be treated with the same drug (tamoxifen or fulvestrant) as the patient has received. We will conduct standard proliferation assays (MTT) assay over a range of doses of the drug as we are aware that intratumoral doses achieved clinically and doses in vitro can be quite different. If successful this analysis would validate the use of such organoid culture to predict patient response in the future. Therefore, we view this analysis as an opportunity to determine proof of principal of such technique and may have wide impact for several studies in the future.

Removal of Subjects

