N/A, Laboratory research will be conducted on tumor specimens obtained as part of routine standard care.

Following examination by the study pathologist of the Ki67 immunohistochemically stained sections and an additional section stained with H&E, areas of viable tumor tissue within the cores will be identified, the extent of antibody staining assessed using appropriate protocols for digital image capture and analysis. It is our expectation that the cores will show considerable intratumoral heterogeneity in the extent of staining and that individual strongly staining nuclei may be interspersed among weakly or negatively

Comparison in the Change of Proliferation Index between Fulvestrant and Tamoxifen in Cyclin D1 +, Estrogen Receptor + Breast Cancer

[name], PI

Essential Elements

#13, 09/13/2017

stained cells. In order to address the problem of intratumoral heterogeneity, we will obtain digital images of the entire tissue section and determine the number of positively stained nuclei per 100,000 μm^2 of viable tumor tissue

The intensity and distribution of cyclin D1 staining will be semiquantitatively scored using the Allred scoring method. The intensity of the immunohistochemical reaction by light microscopy will be recorded as 0 (negative) when no staining of the nuclei is seen even at high magnification, 1+ (weak) if staining is visible only at high magnification, 2+ (moderate when staining is readily visible at low magnification and 3+ (strong) if staining is strikingly positive even at low power magnification. The extent of tumor cell nuclei showing positive staining will be scored as 0 (<10%), 1 (11-25%), 2 (26-50%), 3 (51-75%), 4 (76-90%), and 5 (>90%). Scores for intensity and extent will then be totaled to assign a tumor as having negative (0), weak (1 to 3), moderate (4 to 6), or strong (7 to 8) cyclin D1 expression as has been standardized by Reis-Filho and colleagues. A total score of greater than or equal to 5 will be used as the cut off for cyclin D1 positivity as per the retrospective study conducted by [name] and colleagues.

In addition, manual scoring of cyclinD1, STAT3, STAT5 and Ki67 will also be performed. The manual scoring will be performed as described previously where a score for percentage of cells stained and a score for intensity of scoring is obtained and then added to obtain an Allred score.

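### Cultures from surgical tissue already exposed to study drug can show concordance but cannot validate a predictive test; culture source and signature specimen need reconciling

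*Combined protocol and SAP*

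**What the plan says.** **Culture claim.** Secondary Objectives, Correlative Laboratory Research and Correlatives/Special Studies all state that, if successful, "this analysis would validate the use of such organoid culture to predict patient response in the future". In each place the next sentence calls the work a proof of principle.

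**Culture tissue.** The two laboratory sections take a portion of the surgical specimen from tumours over 1 cm: "half will be frozen for subsequent RNA extraction and expression profiling, and half will be utilized for primary tissue culture". On timing, Study Procedures says that after the "14 day study regimen is complete, the subjects will move on to definitive excisional surgery, between day 15 to day 18". In vitro, "cells in culture will be treated with the same drug (tamoxifen or fulvestrant) as the patient has received". The Study Summary instead proposes "ex-vivo expansion of primary culture from only a few cancer cells obtained by fine needle biopsy" and adds that "it may serve as a proof of principle to maximize the use of biopsy material to predict treatment response".

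**Culture analysis.** In the SAP's Data Analysis section, "Correlations between in vitro assay results and patient assay results will be examined by Pearson correlation or Spearman correlation", with regression for dose response.

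**Signatures.** After reserving frozen surgical tissue for expression profiling, the laboratory sections describe the nanostring assay on RNA from paraffin sections. They do not say whether those sections are from the diagnostic core or the surgical block. Data Analysis promises signatures for every patient. It then compares patients with responsive and resistant signatures on Ki67 change, by stratified ANCOVA.

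**The concern.** A predictive test is run before treatment, on tissue the drug has not reached. The laboratory sections describe the opposite sequence: treat the patient, remove the tumour, culture it, and apply the same drug again. If the culture result then agrees with the patient's response, the agreement concerns cells that have already been through treatment. It does not show what a culture grown from the diagnostic biopsy would have predicted.

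The signature analysis raises a related question. Grouping patients by a baseline characteristic and comparing their Ki67 change is interpretable. Grouping them by something measured after treatment is not interpretable in the same way, because the group may itself be a result of the drug. Without the specimen and time point, a reader cannot tell which analysis was done.

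At stake is what two of the four secondary objectives (signatures, and in vitro against in vivo response) can conclude.

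**Working it through.** The plan gives no figure on this point and no arithmetic applies. The check sets the relevant sections side by side.

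**Step 1: what tissue is cultured, and when is it removed?**

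| Section | Source of cultured cells | Time point |
|---|---|---|
| Study Summary | Fine needle biopsy | Not given; the stated purpose is prediction from biopsy material |
| Correlative Laboratory Research; Correlatives/Special Studies | Portion of the surgical specimen, tumours over 1 cm | Days 15 to 18, after the regimen (Study Procedures) |
| Study Procedures; Time and Events | No fine needle biopsy listed | The only pre-treatment specimen described is the routine diagnostic core |

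The Summary and the laboratory sections disagree. Only the surgical source has a procedure behind it.

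**Step 2: does exposure matter by the protocol's own account?** Yes. The laboratory sections predict reduced nuclear ER and reduced PR in post-treatment fulvestrant specimens. The Background cites a window trial of the same two regimens in premenopausal women, with significant falls in ER and Ki67 on both drugs. The protocol therefore expects post-treatment tumour to differ from the diagnostic tumour, including in the receptor that both drugs act on.

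**Step 3: what can the planned correlation show?** On the surgical source, it relates the patient's response to the in vitro response of cells already exposed to the same drug. A high correlation would show concordance under those conditions. Validating prediction needs the in vitro result to come from pre-treatment cells, and no procedure supplies such a culture.

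**Step 4: what is the signature measured on?**

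| Text | Material | Pre- or post-treatment |
|---|---|---|
| Laboratory sections, paragraph on dividing the specimen | Frozen surgical tissue, tumours over 1 cm | Post |
| Laboratory sections, next paragraph; Secondary Objectives | Paraffin sections | Not stated |
| Data Analysis | Not named; every patient to have a signature | Not stated |

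If the paraffin sections are from the core, the grouping in Data Analysis is by a baseline factor. If they are surgical, both the signature and the post-treatment Ki67 are measured after exposure. An association could then arise because the drug changed both. The text allows either reading.

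**The case against.** The strongest reply is that the protocol already qualifies itself. The sentence after the validation claim calls the work a proof of principle, cultures are planned only when samples are available, and the analysis is a correlation and a dose-response regression. No section commits the investigators to reporting a validated predictive test. That is fair, and it is why the point is small. It does not remove the validation sentence, which appears three times and claims more than the specimen can support.

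On signatures, the objectives ask whether signatures are observed and whether they characterise resistant or sensitive tumours. The Summary also lists signatures among the ways response will be evaluated, which is read-out language. The plan does not say outright that a signature predicts response. That stands. The request for a time point also stands, because Data Analysis uses the signature as a grouping factor.

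A reader might infer stronger points that the documents do not support:

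- *That the signature specimen is not stated at all.* Frozen surgical tissue and paraffin sections are both named. The defect is inconsistency and a missing time point.
- *That the 1 cm limit certainly conflicts with signatures for every patient, given eligibility from 5 mm.* It does so only if frozen tissue is assayed. Paraffin sections carry no such limit.
- *That pre-treatment culture is ruled out because* "Laboratory research will be conducted on tumor specimens obtained as part of routine standard care". The diagnostic core is itself a routine-care specimen, so this sentence does not exclude it.

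**Conclusion.** The concern holds as a minor point confined to secondary objectives. As the laboratory sections stand, the culture analysis can show concordance in drug-exposed cells and cannot validate organoid culture as a predictor. The Study Summary contradicts those sections on tissue source. The signature material is inconsistent and its time point is missing, so the signature comparison of Ki67 change cannot be interpreted until the specimen is named.

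The conclusion on cultures assumes that the laboratory sections govern over the Summary. The Study Treatment Plan heading refers to an attachment that is not among the documents. Even if it described a biopsy, the Summary and the laboratory sections would still need reconciling.

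The documents give no basis for sizing the effect of prior exposure on either analysis, so no figure is offered. It would also go too far to infer that the primary Ki67 comparison or patient safety is affected; neither depends on the cultures or signatures.

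**What to change.** 1. **Culture claim.** In Secondary Objectives, Correlative Laboratory Research and Correlatives/Special Studies, replace the validation sentence with: *If successful, this analysis would show concordance between in vivo response and the in vitro response of cells already exposed to the study drug.* Keep the proof-of-principle sentence. Cost: wording only.
2. **Culture source.** Reconcile the Study Summary with the two laboratory sections. If no pre-treatment tissue will be cultured, remove prediction from biopsy material. Cost: wording only.
3. **Signature specimen.** Name one material and time point consistently in the objectives, Data Analysis and laboratory sections. For the grouping in Data Analysis, use paraffin sections from the pre-treatment core where RNA suffices, and report the number of patients analysed. Report any signature from the surgical specimen only as a post-treatment read-out. Cost: wording plus core sections. Core tissue is limited and already has to supply cyclin D1 and Ki67. Some patients may therefore lack a baseline signature, and the promise of signatures for every patient may need changing.

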1.0 STUDY MANAGEMENT

1.1 Conflict of Interest

Any research personnel who has a conflict of interest with this study (patent ownership, intellectual property, royalties, or financial gain greater than the minimum allowable by their institution, etc.) must declare their conflict of interest to the appropriate institutional review bodies. Local institutional conflict of interest policies will be followed for all research personnel associated with the research project.

11.2 Institutional Review Board (IRB) Approval and Consent

It is expected that the IRB will have the proper representation and function in accordance with federally mandated regulations. The IRB will approve the consent form and protocol.

In obtaining and documenting informed consent, the investigator will comply with the applicable regulatory requirement(s), and will adhere to Good Clinical Practice (GCP) and to ethical principles that have their origin in the Declaration of Helsinki.

Before recruitment and enrollment onto this study, the patient will be given a full explanation of the study and will be given the opportunity to review the consent form. Each consent form must include all the relevant elements currently required by the FDA Regulations and local or state regulations. Once this essential information has been provided to the patient and the investigator is assured that the patient understands the implications of participating in the study, the patient will be asked to give consent to participate in the study by signing an IRB-approved consent form.

Prior to a patient's participation in the trial, the written informed consent form will be signed and personally dated by the patient and by the person who conducted the informed consent discussion.

1.3 Required Documentation

This is not a multi-institutional site study coordinated by MSSM.

